## MSSM Protocol Template HRP-503a

### Instructions:

1. Prepare a document with the following sections. Note that, depending on the nature of your research, certain sections below may not be applicable. Indicate N/A as appropriate, explaining where possible.
2. For any items described in the sponsor's protocol, grant application or other source documents submitted with the application, you may reference the title and page numbers of these documents rather than cutting and pasting into this document. **Do NOT refer to any derived documents, such as the Sample Consent document, or other internal documents required with the submission.**
3. If you reference page numbers, attach those pages to this protocol.
4. When you write a protocol, keep an electronic copy. You will need to modify this copy when making changes.

### Brief Summary of Research (250-400 words):

#### 1) Objectives:

Converging evidence suggests that patients with bipolar disorder suffer from deficits in neurocognitive functioning that persist, despite remission of acute affective symptoms. These impairments contribute directly to functional disability, highlighting the need for interventions above and beyond standard treatments in order to achieve a full inter-episode recovery. The current study aims to investigate the safety and efficacy of a dopamine agonist (pramipexole), on these persistent cognitive abnormalities in euthymic bipolar patients using a placebo-controlled, adjunctive, 12-week trial design.

#### **Aim 1: Baseline to Week 6**

a) To determine the short-term efficacy of pramipexole on neurocognitive functioning in stable BD patients. b) To determine the short-term safety of pramipexole on neurocognitive functioning in stable BD patients.

#### **Aim 2: Week 6 to Week 12**

a) To determine the long-term efficacy of pramipexole on neurocognitive functioning in stable BD patients. b) To determine the long-term safety of pramipexole on neurocognitive functioning in stable BD patients.

**Exploratory Aim:** To integrate results from multiple dopamine-based domains (cognition; affect; reward processing) to evaluate the main and interactive effects of pramipexole on these factors in stable BD patients.

|   |   |   |
|---|---|---|
|  | Protocol Title:                           | 1/2-Prampipexole in Bipolar Disorder: Targeting Cognition (PRAM-BD) |
|   | Principal Investigator Name/Contact Info: | [name]  |
|   | Primary Contact Name/Contact Info:        | [name]
[contact]                           |
|   | Date Revised:                             | March 23, 2016 – date of IRB approval May 6, 2017                   |
|   | Study Number:                             | GCO 13-0237, HS 14-00328  |

## 2) Background

Data suggest that, as in schizophrenia (SZ), bipolar disorder (BD) patients' everyday functioning is directly influenced by persistent symptomatology and cognitive dysfunction (Bowie et al. 2010; [name] et al. 2010). A recent meta-analysis indicated significant correlations (mean  $r=.27$ ) between cognition and functional measures in BD (Depp et al. 2012), with little evidence for differences across cognitive domains. These data strongly support the role of cognition in quality of life in BD and highlight the need for treatment and prevention efforts targeting this domain ([name] et al. 2007). There are several ongoing large-scale clinical trials targeting cognition in SZ, with a parallel need existing in BD. We recently completed one of the first controlled trials of cognition as a treatment target in BD ([name] et al. 2012). We approached the initial question of which agent to test based upon prior evidence that enhancing dopamine may result in improvements in neurocognition in other clinical samples.

Although the neurobiological basis of persistent cognitive impairment in BD is not well-understood, convergent evidence suggests that the enhancement of DA activity may be a useful remediation strategy. Neuroimaging studies highlight structural brain abnormalities in BD in regions rich in DA receptors, including anterior cingulate, dorsolateral, orbital, and subgenual cortex (Drevets et al. 1998; Lopez-Larson et al. 2002) and the basal ganglia (Baumann et al. 2001). Abnormal activation in these regions has been reported in BD during cognitive tasks using fMRI (Blumberg et al. 2000; Gruber et al. 2004). Moreover, in previous studies of healthy subjects increasing levels of DA via agents such as pergolide, a D1 agonist (Kimberg et al. 2003) or bromocriptine, a D2 agonist, (Kimberg et al. 1997; Luciana et al. 1998) improves cognition, particularly in cognitive domains linked to prefrontal cortex (PFC) functions. Finally, molecular genetic studies support the importance of DA in normal cognitive functions. Several cognitive studies have focused on the gene coding for catechol-o-methyl transferase (COMT), an enzyme responsible for the degradation of catecholamines, including DA, in the PFC (Dickinson et al. 2009). Convergent results demonstrate an association between genetic variation within *COMT* and cognitive function in SZ (Bilder et al. 2002; Egan et al. 2001) and healthy controls ([name] et al. 2002; Tsai et al. 2003). *COMT* has also been implicated in the susceptibility for BD (Kirov et al. 1998; Papolos et al. 1998), including work by our group ([name] et al. 2007). In a sample of 52 Caucasian BD probands and 102 Caucasian healthy controls, we detected a modest but significant association between SNP rs165599 and BD, with the g allele being over-represented in cases vs. controls (OR=2.41; genotypic  $p=0.04$ ; allelic  $p=0.02$ ). We found a relationship between the risk allele at this SNP and poorer performance on verbal memory tasks (California Verbal Learning Test; CVLT Trials 1-5;  $p=0.005$ ;  $\eta^2=0.07$ ) particularly with regard to PFC aspects of learning (CVLT semantic cluster;  $p=0.037$ ;  $\eta^2=0.04$ ) in BD patients and in

|   |   |  |
|---|---|--|
|  | Protocol Title:                           | 1/2-Pramipexole in Bipolar Disorder: Targeting Cognition (PRAM-BD) |
|   | Principal Investigator Name/Contact Info: | [name]   |
|   | Primary Contact Name/Contact Info:        | [name]
[contact]                          |
|   | Date Revised:                             | March 23, 2016 – date of IRB approval May 6, 2017                  |
|   | Study Number:                             | GCO 13-0237, HS 14-00328   |

healthy controls ([name] et al. 2007). In addition to these lines of evidence supporting the use of a DA agent to enhance cognition, recent evidence suggests that pramipexole, a novel D2/D3 agonist, may be an effective adjunctive anti-depressant in BD. Pramipexole (Mirapex®) is an FDA-approved medication for Parkinson’s disease (PD) and restless leg syndrome.

### 3) Setting of the Human Research

The Icahn School of Medicine at Mount Sinai (ISMMS) site has ideal facilities for the proposed study. The research activities will be conducted in the Clinical Neuroscience Center located at [name]. This space, completely renovated in 2014, consists of a seven-room suite with ample space for research staff, interview rooms, and an exam room.

### 4) Resources Available to Conduct the Human Research

Recruitment for this study will be done across Mount Sinai and will include:

#### Psychiatry Outpatient Clinic

The Mount Sinai Psychiatry outpatient department (OPD) serves a large catchment area that includes both an affluent neighborhood on the Upper East Side of Manhattan and an economically challenged neighborhood in East Harlem. Mount Sinai is the primary provider of medical care (and mental health care) for many area residents. On a monthly basis, approximately 60 new patients are seen in the adult OPD, of whom 40% have a diagnosis of mood disorder. Approximately 90 subjects with bipolar disorder are currently treated in the OPD; 82 new intakes per year have a diagnosis of bipolar disorder. Any patient referred to the Mount Sinai Psychiatry Outpatient Clinic is presented at intake meetings and research eligible patients are referred to a research psychiatrist in MAP.

#### Mood and Anxiety Disorders Program (MAP)

The Mood and Anxiety Disorders Program (Director: [name].; Co-I on this study) is one of the major research and clinical programs of the Department of Psychiatry.

Referrals are anticipated for the proposed study from the following sources: (1) patients with bipolar disorder currently receiving treatment in the MAP program; (2) the Mount Sinai Hospital Adult Outpatient Psychiatry Department; (3) self-referrals from patients who have completed other research protocols in the MAP program; (4) clinicians within

|   |   |  |
|---|---|--|
|  | Protocol Title:                           | 1/2-Pramipexole in Bipolar Disorder: Targeting Cognition (PRAM-BD) |
|   | Principal Investigator Name/Contact Info: | [name]   |
|   | Primary Contact Name/Contact Info:        | [name]
[contact]                          |
|   | Date Revised:                             | March 23, 2016 – date of IRB approval May 6, 2017                  |
|   | Study Number:                             | GCO 13-0237, HS 14-00328   |

and outside of the Mount Sinai Hospital system, including affiliates with large numbers of underserved patients such as Elmhurst Hospital in Queens; (5) self-referrals from individuals attending presentations on bipolar disorder in the New York State and tri-state area and from media advertisements. In addition, we anticipate the receipt of referrals from consumer advocacy groups specializing in severe, treatment resistant mood disorders, including NAMI and the Mood Disorders Support Group (MDSG) of New York.

## 5) Study Design

### a) Recruitment Methods

Subjects will be recruited from MAP and the OPD as described above. Community advertisements will be placed if needed (none currently attached for review). Potentially eligible patients are identified by the patient’s clinical care taker (nurse practitioner and/or physician), who would then ask the patient’s permission for our research team to approach and explain the protocol. A research member will approach that individual and explain the study objectives, procedures, risks and benefits, and begin the informed consent process if the patient wishes.

### b) Inclusion and Exclusion Criteria

**Inclusion criteria:** 1. Age 18-65. 2. DSM-IV BD I or II diagnosis. 3. Affective stability, defined by a Young Mania Rating Scale (YMRS) rating of < 8 and a Hamilton Depression Rating Scale (HRSD) rating of  $\leq 16$  at screening and baseline. We will further require that any subsyndromal depression has not significantly worsened in the 4 weeks prior to randomization so as to avoid enrolling subjects who are on the verge of a full depressive episode. 4. Evidence of clinically-significant neurocognitive impairment at screening. This will be formally assessed using a short battery of tests including Trails B, Wechsler Adult Intelligence Scale (WAIS-IV) Digit Symbol, WAIS-IV Digit Span Forward and Backward, Wisconsin Card Sorting Test (WCST), and California Verbal Learning Test – Second Edition (CVLT-II). Clinically-significant impairment will be defined as scoring  $\geq 1$  SD below normative means on at least one of these measures. 5. Clinically-acceptable, stably-dosed, mood stabilizing medication regimen for  $\geq 1$  month prior to enrollment, with no medication changes planned over the 12-week study period.

**Exclusion criteria:** 1. History of CNS trauma, neurological disorder, ADHD, or learning disability. 2. Positive urine toxicology or DSM-IV diagnosis of substance abuse/dependence within 3 months. 3. Active, unstable medical problem that may interfere with cognition. 4. Recent history of rapid-cycling. 5. Abnormal lab or ECG result at screen. 6. History of heart failure. 7. Significant suicidal risk (HRSD item 3 > 2 or by clinical judgment). 8. Estimated IQ in MR range as per Wide Range Achievement Test (WRAT) standard score of less than 70. 9. Pregnant women or women of child

|   |   |  |
|---|---|--|
|  | Protocol Title:                           | 1/2-Pramipexole in Bipolar Disorder: Targeting Cognition (PRAM-BD) |
|   | Principal Investigator Name/Contact Info: | [name]   |
|   | Primary Contact Name/Contact Info:        | [name]
[contact]                          |
|   | Date Revised:                             | March 23, 2016 – date of IRB approval May 6, 2017                  |
|   | Study Number:                             | GCO 13-0237, HS 14-00328   |

bearing potential who are not using a medically accepted means of contraception (including oral contraceptive or implant, condom, diaphragm, spermicide, intrauterine device, tubal ligation, or partner with vasectomy) **10.** Women who are breastfeeding. **11.** Participation in any other investigational cognitive enhancement study within 30 days.

**Concomitant Medications:** Practical and ethical considerations prevent a focus on medication-free patients. Medications with known adverse cognitive effects will be disallowed (i.e., topiramate, anticholinergics), as will agents that may enhance cognition (e.g., amphetamine, other DA agonists). Benzodiazepines will not be allowed within 6 hours of testing. ECT in the past 12 months will be disallowed, as will any drug known to interact with pramipexole. With regard to antipsychotic medications specifically, only half of the sample will be allowed to be taking any antipsychotics. Recruitment efforts will be adjusted to ensure 50% of the sample is antipsychotic-free at baseline. Further, we will exclude any subject who is taking more than 4 concomitant psychotropic medications. Older generation neuroleptics will be specifically disallowed due to their high binding potential at the D2 receptor (Kapur et al. 1999). Although some of the standard treatments for BD (e.g. lithium) may influence cognition, it is impractical to exclude these medications given their widespread use; therefore, data will be coded for medication classes and dosages to determine a load score (as per Hassel et al. 2008) to be included as a covariate in statistical analyses.

### c) Number of Subjects

Up to 50 affectively stable patients with Bipolar Disorder will be randomized via recruitment through MAP, the Mount Sinai OPD, and community advertisements if necessary. Additional subjects will be screened, with an assumption of some not meeting eligibility; therefore, we estimate 70 patients to be consented for 50 to be randomized.

### d) Study Timelines

There will be a 2-month start-up, 28 months of recruitment and 6 months of follow-up. The last patient randomized will be mid-way through Year 2 to ensure study completion by end of Year 3. Analyses and manuscript preparation will be completed immediately thereafter. We will screen ~3 patients per month (~1 patient randomized/month), totaling 70 patients screened and 50 patients randomized.

### e) Study Endpoints

The primary endpoints related to the safety and efficacy on neurocognitive functioning of pramipexole will be measured. Neurocognitive performance on the MATRICS Consensus Cognitive Battery will be measured at baseline, week 6, and 12 (or end of study). Safety measures will be assessed at each visit throughout the study. Co-primary measures of everyday functioning (described below) will be assessed at baseline and week 12 (or end of study).

|   |   |  |
|---|---|--|
|  | Protocol Title:                           | 1/2-Pramipexole in Bipolar Disorder: Targeting Cognition (PRAM-BD) |
|   | Principal Investigator Name/Contact Info: | [name]   |
|   | Primary Contact Name/Contact Info:        | [name]
[contact]                          |
|   | Date Revised:                             | March 23, 2016 – date of IRB approval May 6, 2017                  |
|   | Study Number:                             | GCO 13-0237, HS 14-00328   |

## f) Procedures Involved in the Human Research

All eligible participants will undergo study visits at screening, baseline (week 0), week 1, week 2, week 3, week 4, week 6, week 8, and week 12, (end of study).

Randomization will be conducted via a computer generated program and all study staff will be blinded unless un-blinding is required for safety reasons. Subjects will be randomized on a 1:1 ratio with stratification for concomitant antipsychotic status and depression at baseline (HRSD <8 vs  $\geq$  8). Study drug will be blinded and matched to placebo. Adapting from our previous work in BD and according to package labeling, the dosage titration schedule will be slow and flexible. Dosing will be initiated at 0.25 mg QHS on night one, followed by 0.25 mg BID day two onward, and increased every week to a target of 4.5 mg/day. As compared with our previous maximum 1.5 mg/day ([name] et al. 2012), we opted to allow up to 4.5 mg/day (the maximum approved dosage in Parkinson’s disease) to ensure adequate target engagement. We are familiar with this dose range, as 4.5 mg/day was allowed in our study in BD depression (Goldberg et al. 2004). Dosing will be flexible based on side effects; however, if 1.5 mg/day cannot be tolerated, the subject will be discontinued. Titration will occur up to week 6 and then efforts will be made to maintain the same dose until the completion of the trial (week 12).

Measures are described in detail below:

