Data from this study may be used in medical publications or presentations. The information will be de-identified so that individual subjects cannot be recognized and the information will no longer be considered PHI. The information that is collected for research will be analyzed for many years and it is not possible to know how long this

|   |   |  |
|---|---|--|
|  | Protocol Title:                           | 1/2-Pramipexole in Bipolar Disorder: Targeting Cognition (PRAM-BD) |
|   | Principal Investigator Name/Contact Info: | [name]   |
|   | Primary Contact Name/Contact Info:        | [name]
[contact]                          |
|   | Date Revised:                             | March 23, 2016 – date of IRB approval May 6, 2017                  |
|   | Study Number:                             | GCO 13-0237, HS 14-00328   |

analysis and follow-up will take. Therefore, participants are allowing access to this information indefinitely.

Participants will only be identified with a numerical code in compliance with HIPAA regulations. Raw subject data will be secured in double locked physical control. Digitized raw data will be similarly de-identified using coding and will be secured on an MS SQL server with Windows-integrated security.

**Statistical Methods: Preliminary analyses:** Groups will be compared on demographics, baseline symptom ratings, and concomitant medication load; if necessary, covariates will be included in subsequent models. MCCB data are standardized using the MCCB program, scores are age- and sex- corrected and reported on a t-score scale (Mean=50, SD=10). Any study focusing on improving cognition must consider practice effects (Goldberg et al. 2008). The placebo arm will provide estimates of expected practice so that we are able to calculate a reliable change index (RCI) to determine the meaningfulness of change (Goldberg et al. 2009).

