|   | Study Number:                             | GCO 13-0237, HS 14-00328   |

patients on pramipexole vs. patients on placebo. This will be tested in an intent-to-treat analysis using a 0.05 level two-tailed test based on a mixed effects regression model, with patients considered to be a random effect, and randomization group a fixed effect. In order to preserve statistical power, change in MCCB Composite will be used as the dependent variable; however, secondary analyses will be conducted for MCCB domain scores and measure of reward processing. The use of two post baseline evaluations (weeks 6 and 12) and the ability of the model to incorporate all available data, also improves efficiency (i.e., power). This approach will also be employed in subsequent comparisons of specific domains and for measures of reward processing. These additional analyses will be conducted at a nominal 0.05 level and will focus on enhancing interpretation of the primary analysis by highlighting the specific domains most affected by pramipexole. Since randomization is stratified by concomitant antipsychotic use and baseline depression status, indicators of stratification will be included in the model as fixed effects.

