**Sample size/Power:** A total of one hundred patients will be randomized 1:1 (50 from ISMMS, 50 from ZHH). The adequacy of this sample size is based on the ability to reject the null hypotheses of no difference between treatment groups with respect to the MCCB composite score with sufficient power (80%). Ideally, sample size would be determined to ensure adequate power to detect the minimal clinically important difference. No specific guidelines exist to establish such a threshold in this setting but cognitive change of at least a moderate effect would likely be necessary to allow for clinical meaningfulness. Our sample size provides approximately 80% power to detect a standardized difference (e.g., Cohen’s d) of approximately 0.55 with a two-tailed 0.05 level test. For the pre-specified subgroup analysis based on concomitant use at baseline, the detectable standardized difference is about 0.80.

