### **15) Multi-Site Human Research (Coordinating Center)**

The overall organization of this project is provided by the PIs, Drs. [name] and [name]. Each site [Icahn School of Medicine at Mount Sinai (ISMMS) and the Zucker Hillside Hospital (ZHH)] will be responsible for managing the activities of their site. Overall organization and management of sites will be provided by ISMMS. All PIs and Co-Is will participate in monthly conference calls over the first 2.5 years of the study. During the data analytic phase, the frequency of conference calls will be increased to weekly.

|   |   |  |
|---|---|--|
|  | Protocol Title:                           | 1/2-Pramipexole in Bipolar Disorder: Targeting Cognition (PRAM-BD) |
|   | Principal Investigator Name/Contact Info: | [name]   |
|   | Primary Contact Name/Contact Info:        | [name]
[contact]                          |
|   | Date Revised:                             | March 23, 2016 – date of IRB approval May 6, 2017                  |
|   | Study Number:                             | GCO 13-0237, HS 14-00328   |

Mount Sinai will serve as the coordinating site for this trial; therefore, [name] will be the contact PI and responsible for all interactions between sites and with NIH. All procedures specific to the clinical trial will be identical at the two sites. Rater training will be initiated with an in-person, on-site meeting to ensure adequate reliability for clinical and neurocognitive assessments. We are uniquely situated to ensure reliability, as [name] was formerly the Director of the Neurocognitive Assessment Unit at the second site (ZHH) and she conducted training with staff at both sites. All statistical analyses will be led by the statistician (Co-I) [name] from ISMMS. This will include intermittent safety data analyses for the Data Safety and Monitoring Committee (DSMB) review and all analyses at the conclusion of the trial.

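### Site is neither a randomisation stratum nor a model term in a trial that randomises 50 patients at each of two sites; adding it is a cheap, modest gain in precision

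*Combined protocol and SAP*

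**What the plan says.** All references are to the combined protocol and SAP.

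- **Sites.** Section 5(h), Sample size/Power: "A total of one hundred patients will be randomized 1:1 (50 from ISMMS, 50 from ZHH".
- **Mechanism.** Section 5(f): "Randomization will be conducted via a computer generated program". It does not say whether there is one list for the trial or one per site.
- **Strata.** Section 5(f): "Subjects will be randomized on a 1:1 ratio with stratification for concomitant antipsychotic status and depression at baseline". The depression split is at an HRSD of 8. Site is not listed.
- **Model.** Section 5(h), Primary hypothesis testing, describes a mixed model of change in MCCB composite "with patients considered to be a random effect, and randomization group a fixed effect". It adds that "indicators of stratification will be included in the model as fixed effects", and the factors it names are antipsychotic use and baseline depression.
- **Other covariates.** Section 5(h), Preliminary analyses: "Groups will be compared on demographics, baseline symptom ratings, and concomitant medication load; if necessary, covariates will be included in subsequent models". Site is not among the items compared.
- **Coordination.** Section 15 makes each site responsible for its own activities. It also gives overall management to the coordinating site, requires the same trial procedures at both, and describes joint rater training.

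**The concern.** With only two sites, one binary factor divides the sample in half, and nothing in the allocation or the analysis takes account of it. The endpoint is a change score, so a stable difference between sites in the level of MCCB performance cancels. A difference in change does not. The plan itself points to possible sources: practice effects, dosing that is flexible according to side effects, and discontinuation. The recruitment sections describe only the coordinating site's sources, so case mix at the other site may differ.

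What is at stake depends on the unstated mechanism. With a central list, the arms can differ by chance in their mix of sites, and the planned model would leave that in the estimate and in the residual variance. With separate lists, the arms are close to balanced by site, but the model ignores a factor on which allocation was in effect stratified. That departs from the plan's own rule of carrying stratification factors into the model.

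**Working it through.** **Inputs.** From the documents: 100 patients, 50 per site, 1:1 allocation, two-sided 0.05, target standardised difference 0.55. Not in the documents: the site difference in mean MCCB change, s, in within-site SDs. I assume 0.3 to 0.5, with 0 and 1.0 as outer values. The calculations use a two-arm comparison of change with 50 per arm; they ignore the week 12 data, attrition and the two planned strata.

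**1. The plan's own figures.** The standard error of the difference is √(2/50) = 0.20. Power is Φ(0.55/0.20 − 1.96) = Φ(0.79) = 78.5% (t test: 77.7%), against a stated figure of about 80%. For a subgroup with 25 per arm, the detectable difference is (1.96 + 0.84) × √(2/25) = 0.79 (t test: 0.81), against a stated 0.80. Both reproduce.

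**2. Chance imbalance with a central list.** The number of one site's patients in the pramipexole arm is hypergeometric (100, 50, 50), with variance 50 × 0.5 × 0.5 × 50/99 = 6.31 and SD 2.51.
- 28 v 22 or worse: 31.7%
- 29 v 21 or worse: 16.1%
- 30 v 20 or worse: 7.1%

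**3. Shift in the estimate.** For a 30/20 split the shift is s × (30/50 − 20/50) = 0.2s. That is 0.06 at s = 0.3 and 0.10 at s = 0.5, or 11% and 18% of 0.55. A one-SD imbalance (a 0.10 difference in proportions) gives half as much, 0.03 to 0.05, against a standard error of 0.20.

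**4. Precision with a central list.** Omitting site multiplies the variance by 1 + s²/4, so the effective difference is 0.55/√(1 + s²/4).

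| s | Variance factor | Effective d | Power without site (t test) |
|---|---|---|---|
| 0 | 1.0000 | 0.550 | 77.7% |
| 0.3 | 1.0225 | 0.544 | 76.8% |
| 0.5 | 1.0625 | 0.534 | 75.2% |
| 1.0 | 1.2500 | 0.492 | 68.3% |

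With a site fixed effect, simulated power stays at about 77% to 79% for every s. The loss from omission is therefore 77.7 − 76.8 = 0.9 points at 0.3 and 77.7 − 75.2 = 2.5 points at 0.5.

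**5. Type I error with a central list.** Averaged over allocations, simulation gives 5.0% to 5.1% without a site term for s from 0.3 to 1.0. Given a 30/20 split, it is 5.8% at s = 0.3 and 7.0% at s = 0.5.

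**6. Per-site lists, site omitted from the model.** The estimate is balanced by site but its standard error is too large by the factor √(1 + s²/4). Type I error is 2 × [1 − Φ(1.96 × √(1 + s²/4))]. At s = 0.3 the argument is 1.982, giving 4.7%; at s = 0.5 it is 2.020, giving 4.3%. At s = 0.5 a simulation of 8,000 trials gave 3.8% (Monte Carlo standard error 0.2 points) and one of 400,000 trials gave 4.3%. I take 4.3%. With a site term the rate returns to about 5%.

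**The case against.** The strongest reply is that the effect is small and its main input is assumed. No site difference is documented, level differences cancel in a change score, MCCB scores are age- and sex-corrected, and section 15 promises common procedures and rater training. The 30/20 split is a tail event. Chance imbalance is already covered by the nominal error rate, so inference is not invalid. All of this stands, and it limits the point to a refinement. It does not remove it: common procedures do not equalise case mix, dose reached or dropout, and the stated power has no slack.

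Three stronger readings are tempting, and the documents do not support them.

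- **That the antipsychotic subgroup result would be largely a comparison of sites.** The stated 0.80 matches drug v placebo with 25 per arm inside a subgroup. That comparison is randomised and stratified on antipsychotic status. Even with 35/50 users at one site and 15/50 at the other, the correlation between site and use is (35 × 35 − 15 × 15)/(50 × 50) = 0.4, or 16% shared variance. Confounding of the difference between subgroup effects would also need the treatment effect to vary by site, which a site main effect would not correct.
- **That the antipsychotic limit needs to be set per site.** Section 5(b) says "only half of the sample will be allowed to be taking any antipsychotics". This is one site's protocol, with up to 50 patients in section 5(c), so the sample may mean those 50 or the full 100. The text does not settle it.
- **That the sites run independently.** Section 15 does say each site "will be responsible for managing the activities of their site", but it also provides for overall management by the coordinating site, identical trial procedures and regular joint calls.

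**Conclusion.** The omission is clear from sections 5(f) and 5(h): site is not a stratum, a model term or a named covariate. The consequence is modest. With a central list, the cost is lost precision and the chance of a shifted estimate in the one allocation actually drawn: about 1 to 2.5 points of power, and 0.06 to 0.10 SD under a 30/20 split that has a 7% chance of being reached or exceeded. With per-site lists, the cost is a slightly conservative test. These sizes rest on an assumed site difference of 0.3 to 0.5 SD in MCCB change; below 0.3 the loss of power is under one point. A reader might infer an inflated overall type I error, but averaged over allocations it stays near 5%. The change is worth making because it is cheap and helps under either mechanism.

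**What to change.** 1. **Section 5(h), Primary hypothesis testing.** Add site (ISMMS, ZHH) as a fixed effect in the primary, secondary and subgroup models, fixed before unblinding. Report the treatment effect by site descriptively. Two sites are too few for a random site effect.
2. **Section 5(f).** State whether the list is central or per site. If randomisation has not begun, add site as a third stratification factor with small blocks: 2 × 2 × 2 = 8 strata, about 12 patients each (100/8 = 12.5). If it has begun, the model term alone still recovers most of the precision. Stratifying without the model term should be avoided, since that is the conservative case shown in step 6.

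The cost is one degree of freedom in the model and some incomplete blocks at the end of accrual.
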